10.4 OBLIGATION OF THE INVESTIGATOR REGARDING SAFETY REPORTING

10.4.1 Definitions of adverse events

10.4.1.1 Adverse event

An **adverse event** (AE) is any untoward medical occurrence in a patient or clinical investigation patient administered a pharmaceutical product and which does not necessarily have to have a causal relationship with this treatment.

10.4.1.2 Serious adverse event

A **serious adverse event** (SAE) is any untoward medical occurrence that at any dose:

- Results in death, or
- Is life-threatening, or

Note: The term "life-threatening" in the definition of "serious" refers to an event in which the patient was at risk of death at the time of the event; it does not refer to an event which hypothetically might have caused death if it were more severe.

- Requires inpatient hospitalization or prolongation of existing hospitalization, or
- Results in persistent or significant disability/incapacity, or
- Is a congenital anomaly/birth defect, or
- Is a medically important event.

Medical and scientific judgment should be exercised in deciding whether expedited reporting is appropriate in other situations, such as important medical events that may not be immediately life-threatening or result in death or hospitalization but may jeopardize the

patient or may require medical or surgical intervention (ie, specific measures or corrective treatment) to prevent one of the other outcomes listed in the definition above.

Note: The following list of medically important events is intended to serve as a guideline for determining which condition has to be considered a medically important event. The list is not intended to be exhaustive:

- Intensive treatment in an emergency room or at home for:
 - Allergic bronchospasm;
 - Blood dyscrasias (ie, agranulocytosis, aplastic anemia, bone marrow aplasia, myelodysplasia, pancytopenia, etc);
 - Convulsions (seizures, epilepsy, epileptic fit, absence, etc).
- Development of drug dependence or drug abuse;
- ALT $>3 \times$ ULN + total bilirubin $>2 \times$ ULN or asymptomatic ALT increase $>10 \times$ ULN;
- Suicide attempt or any event suggestive of suicidality;
- Syncope, loss of consciousness (except if documented as a consequence of blood sampling);
- Bullous cutaneous eruptions;
- Any new invasive ventilatory support (excluding planned ventilatory support less than 3 days duration for a planned surgical procedure).

10.4.1.3 Adverse event of special interest

An adverse event of special interest (AESI) is an AE (serious or nonserious) of scientific and medical concern specific to the Sponsor's product or program, for which ongoing monitoring and immediate notification by the Investigator to the Sponsor is required. Such events may require further investigation in order to characterize and understand them. Adverse events of special interest may be added, modified or removed during a study by protocol amendment.

AESIs will include:

- IARs
 - IARs are defined as AEs that occur during either the infusion or the observation period following the infusion which are deemed to be related or possibly related to the IMP. At the discretion of the Investigator, AEs occurring after completion of the post-infusion observation period that are assessed as related may also be considered IARs. Refer to [Section 10.6](#) for additional testing in the event a patient experiences a moderate, severe, or recurrent IAR suggestive of hypersensitivity reactions and for suggested guidelines for the management of IARs.
- Pregnancy
 - Pregnancy occurring in a female patient included in the clinical trial. Pregnancy will be recorded as an AESI with immediate notification in all cases. It will be qualified as an SAE only if it fulfills the SAE criteria.
 - Male patients will be instructed to notify the Investigator immediately if they discover that their sexual partner is pregnant.
 - In the event of pregnancy in a female participant, IMP should be discontinued.

- Follow-up of the pregnancy is mandatory in a female participant or in a female partner of a male participant, until the outcome has been determined.
- Symptomatic overdose (serious or nonserious) with IMP
 - An overdose (accidental or intentional) with the IMP is an event suspected by the Investigator or spontaneously notified by the patient and defined as at least twice the intended dose within the protocol defined therapeutic interval, adjusted according to the tested drug.

Of note, asymptomatic overdose has to be reported as a standard AE, and is not considered an AESI.

- Clinical laboratory (change from baseline)
 - ALT or AST increase of $\geq 3 \times$ ULN if baseline is $<\text{ULN}$, or ALT or AST increase $\geq 2 \times$ the baseline value if baseline is $\geq \text{ULN}$;
 - A maximum ALT value of ≥ 400 IU/L (except if baseline value is ≥ 400 IU/L) or AST value of ≥ 500 IU/L (except if baseline value is ≥ 500 IU) or an increase in direct, indirect, or total bilirubin of $\geq 2 \times$ ULN;
 - Serum creatinine increase of $>1.5 \times$ the baseline value (and final serum creatinine value is $>\text{ULN}$).

In the event of an AESI, the Sponsor will be informed immediately (and within 24 hours), using the AE form together with the SAE complementary form to be entered in the e-CRF.

10.4.2 General guidelines for reporting adverse events

- All AEs, regardless of seriousness or relationship to IMP/NIMP, spanning from the signature of the ICF until the end of the study as defined by the protocol for that patient, are to be recorded on the e-CRF.
- Whenever possible, diagnosis or single syndrome should be reported instead of symptoms. The Investigator should specify the date of onset, intensity, action taken with respect to study treatment, corrective treatment/therapy given, additional investigations performed, outcome, and his/her opinion as to whether there is a reasonable possibility that the AE was caused by the study treatment or by the study procedure(s).
- If the Investigator assesses the AE related to study treatment and the Investigator cannot reasonably explain the AE by other factors (such as clinical state, concomitant therapy, and /or other interventions) or if the cause of the AE is unknown by the Investigator, the relationship to study treatment must be checked "Related" by the Investigator.
- The Investigator should check "Not Related" when there is a clear alternative cause to the event other than the study treatment according to the Investigator.

There is one exception to this rule. In instances where a patient experiences an IAR (refer to [Section 10.6](#)), allergic, or anaphylactic reaction, either during infusion or post observation period, each of the individual signs and/or symptoms comprising the reaction should be captured as individual AE terms.

- The Investigator should take appropriate measures to follow all AEs until clinical recovery is complete and laboratory results have returned to normal, or until progression has been stabilized, or until death, in order to ensure the safety of the patients. This may imply that observations will continue beyond the last planned visit per protocol, and that additional investigations may be requested by the monitoring team up to as noticed by the Sponsor.
- When treatment is prematurely discontinued, the patient's observations will continue until the end of the study as defined by the protocol for that patient.
- Laboratory, vital signs or ECG abnormalities are to be recorded as AEs only if:
 - Symptomatic, and/or
 - Requiring either corrective treatment or consultation, and/or
 - Leading to IMP discontinuation or modification of dosing, and/or
 - Fulfilling a seriousness criterion, and/or
 - Defined as an AESI.

Instructions for AE reporting are summarized in [Table 4](#).

See Appendix C ([Section 17.3.2](#)) for an addendum to this section for Germany only.

10.4.3 Instructions for reporting serious adverse events

In the case of occurrence of an SAE, the Investigator or any designees must immediately:

- ENTER (within 24 hours) the information related to the SAE in the appropriate screens of the e-CRF; the system will automatically send a notification to the monitoring team after approval of the Investigator within the e-CRF or after a standard delay.
- All further data updates should be recorded in the e-CRF as appropriate, within 24 hours of knowledge of the SAE. In addition, every effort should be made to further document any SAE that is fatal or life-threatening within a week (7 days) of the initial notification.
- A back-up plan is available and should be used when the e-CRF system does not work. Please refer to the study manual for further guidance.

Any SAE brought to the attention of the Investigator at any time after the end of the study for the patient and considered by him/her to be caused by the IMP with a reasonable possibility, should be reported to the monitoring team.

10.4.4 Guidelines for reporting adverse events of special interest

For AESIs, the Sponsor must be informed immediately (ie, within 24 hours), as per SAE notification guidelines described in [Section 10.4.3](#), even if not fulfilling a seriousness criterion, using the corresponding pages of the CRF (to be sent) or screens in the e-CRF.

Instructions for AE reporting are summarized in [Table 4](#).

The needs for specific monitoring, documentation, and management of AESIs are described in this section.

For each defined AESI, consider carefully the need to collect additional specific information that would impact the study, such as:

- Pre-existing related condition or lifestyle of interest for the AE (eg, habits, cardiovascular risk factor).
- Expected list of associated signs and symptoms.
- Corrective actions (eg, treatment discontinuation, concomitant treatment).
- Diagnostic actions (eg, test[s] or procedure[s] results).
- Additional descriptive factors.
- Sequelae.
- IARs:
 - Any pre-infusion medication(s) administered;
 - Infusion rate at which the IAR occurred;
 - Time to onset of IAR;
 - Any adjustments to infusion rate made;
 - Any medications and/or therapies administered;
 - Time to IAR resolution (de-challenge);
 - Re-challenge;
 - Relevant vital signs (including pre-infusion vital signs).

10.4.5 Guidelines for management of specific laboratory abnormalities

Decision trees for the management of certain laboratory abnormalities by Sanofi are provided in Appendix B ([Section 17.2](#)).

The following laboratory abnormalities should be monitored, documented, and managed according to the related flow chart in protocol appendices,

- Neutropenia;
- Thrombocytopenia;
- ALT increase;
- Acute renal insufficiency.

Refer to [Section 10.4.1.3](#) for specific laboratory abnormalities that are identified as AESIs.

Table 4 - Summary of adverse event reporting instructions

Event category	Reporting timeframe	Specific events in this category	Case Report Form completion		
			AE form	Safety Complementary Form	Other specific forms
AE (non-SAE, non-AESI)	Routine	Any AE that is not SAE or AESI	Yes	No	No
SAE (non-AESI or AESI)	Expedited (within 24 hours)	Any AE meeting seriousness criterion per Section 10.4.1.2	Yes	Yes	No
AESI	Expedited (within 24 hours)	Death	Yes	Yes	Yes
		IAR	Yes	Yes	No
		Pregnancy	Yes	Yes	Yes
		Symptomatic overdose	Yes	Yes	Yes
		ALT \geq 3 ULN (if baseline ALT<ULN) and ALT \geq 2 x baseline (if baseline ALT \geq ULN)	Yes	Yes	Yes
		AST \geq 3 ULN (if baseline AST<ULN) and AST \geq 2 x baseline (if baseline AST \geq ULN)	Yes	Yes	No
		ALT \geq 400 IU/L (except if baseline value \geq 400 IU/L) or AST \geq 500 IU/L (except if baseline value \geq 500 IU/L), or increase in direct, indirect, or total bilirubin \geq 2 x ULN	Yes	Yes	Yes
Serum creatinine $>1.5 \times$ baseline (if final creatinine $>$ ULN)			Yes	Yes	No

AE = adverse event; SAE = serious adverse event; AESI = adverse event of special interest; IAR = infusion-associated reaction; ALT = alanine aminotransferase; ULN = upper limit of normal; AST = aspartate aminotransferase; IU/L = international units per liter

10.5 OBLIGATIONS OF THE SPONSOR

During the course of the study, the Sponsor will report in an expedited manner:

- All SAEs that are both unexpected and at least reasonably related to the IMP, ie, any suspected unexpected serious adverse reaction (SUSAR), to the regulatory authorities, independent ethics committee (IECs)/institutional review boards (IRBs) as appropriate and to the Investigators.
- All SAEs that are expected and at least reasonably related to the IMPs to the regulatory authorities, according to local regulations.

Adverse events that are considered expected will be specified by the reference safety information (IB for avalglucosidase alfa and label for alglucosidase alfa).

The Sponsor will report all safety observations made during the conduct of the trial in the clinical study report.

10.6 SAFETY INSTRUCTIONS

For management of mild IARs, infusion rate reductions (ie, reduced to half the rate) or temporary interruptions may mitigate the reaction.

Testing for moderate, severe, and recurrent mild IARs will include, if clinically indicated:

- Assessments for circulating immune complex detection; and IgE, serum tryptase, and complement activation, following moderate, severe, or recurrent mild IARs suggestive of hypersensitivity reactions.
- Skin testing if IARs are suggestive of a Type I hypersensitivity reaction (IgE-mediated) as appropriate.

For moderate to severe or recurrent IARs, the Investigator may consider the use of pretreatment medications (ie, antihistamines, antipyretics, and/or glucocorticoids), in addition to infusion rate reductions, interruptions, or even discontinuation, if necessary. Please refer to the IB (Sections 7.1.2 and 7.1.3) for further guidance on the management of IARs.

Moderate, severe, and recurrent mild IARs will be discussed with the DMC. If the DMC recommends or suggests that a desensitization procedure to the IMP could be proposed to the patient, in agreement with the Investigator and the patient's guardian(s), such a procedure may be initiated as per guidelines in the pharmacy manual.

If severe hypersensitivity or anaphylactic reactions occur, immediate discontinuation of the infusion should be considered, and appropriate medical treatment should be initiated. Severe reactions are generally managed with infusion interruption, administration of antihistamines, corticosteroids, IV fluids, and/or oxygen, when clinically indicated. In some cases of anaphylaxis, epinephrine has been administered. Because of the potential for severe infusion reactions, appropriate medical support measures, including cardiopulmonary resuscitation equipment especially for patients with cardiac hypertrophy and patients with significantly compromised respiratory function, should be readily available.

The Investigator will continue to monitor the patient until the parameter returns to baseline or until the Investigator determines that follow-up is no longer medically necessary.

10.7 ADVERSE EVENTS MONITORING

All events will be managed and reported in compliance with all applicable regulations, and included in the final clinical study report.

11 STATISTICAL CONSIDERATIONS

11.1 DETERMINATION OF SAMPLE SIZE

No formal sample size calculations have been performed. Sample size for this study was based upon empirical considerations.

11.2 DISPOSITION OF PATIENTS

Screened patients are defined as any patient who signed the ICF.

For Cohort 3, randomized patients consist of all patients who have been allocated a treatment kit based on the randomization process for participants. Patients treated without being randomized will not be considered as randomized and will not be included in any efficacy population. For any patient randomized more than once, only the data associated with the first randomization will be used in any analysis population. The safety experience associated with any later randomization will be assessed separately.

11.3 ANALYSIS POPULATIONS

Safety population: all patients who received at least 1 infusion (partial or total) in the study.

Modified intent-to-treat (mITT) population: all randomized patients in Cohort 3 who received at least 1 infusion and with evaluable baseline efficacy assessment, analyzed according to the treatment group allocated by randomization.

11.4 STATISTICAL METHODS

11.4.1 Extent of study treatment exposure and compliance

The extent of study drug exposure will be assessed by the duration of study drug exposure, number of infusions, and amount of dose received. The extent of study drug exposure will be summarized in the safety population.

Duration of study drug exposure is defined below:

For the PAP

- Duration of IMP exposure is defined as the first dose date in the extension period (or 14 days after the last dose date in PAP if the patient is not continuing in extension period) minus (–) first dose date in the treatment period, regardless of unplanned intermittent discontinuations.

For the extension period,

- Duration of IMP exposure is defined as 14 days after the last dose in the extension period minus (–) the first dose date in the extension period, regardless of unplanned intermittent discontinuations. This is defined only for Cohort 3 alglucosidase alfa patients who are switched to avalglucosidase alfa and treated in the extension period.

For the overall treatment duration,

- Duration of avalglucosidase alfa total exposure is defined as 14 days after last avalglucosidase alfa dose in study minus (–) first avalglucosidase alfa dose date in the study. This is defined for all patients other than the Cohort 3 alglucosidase alfa patients.

The duration of IMP exposure will be summarized descriptively as a quantitative variable (number, mean, SD, median, minimum, and maximum), as well as categorical variable (eg, <2 months, 2-4 months, 4-6 months for the PAP).

The cumulative dose information for the considered period (PAP or overall treatment period) will be assessed by the total number of infusions received in the considered period, as well as total amount of IMP in mL (if this information is available from the database) received in the considered period. These data will be summarized descriptively.

For Cohorts 1 and 2, and Cohort 3 avalglucosidase alfa patients, both duration of IMP exposure and cumulative dose will be summarized for the PAP, as well as the overall treatment period. For Cohort 3 alglucosidase alfa patients, both duration of IMP exposure and cumulative dose will be summarized for the PAP; in addition, duration of IMP exposure will be summarized for the extension period after switching to avalglucosidase alfa.

11.4.1.1 Compliance

A given administration will be considered noncompliant if the patient did not take the planned dose of treatment as required by the protocol. Compliance to the treatment regimen will be monitored by site personnel during the study.

Treatment compliance for the PAP and the extension period respectively will be summarized descriptively as quantitative variable using the safety population. The number and percentage of patients with noncompliance (missed 2 or more consecutive infusions not for safety cause, or missed $\geq 20\%$ of total doses in the treatment or extension period) will be provided.

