- e Retrospective chart review at screening/baseline to collect available data on clinical decline or sub-optimal clinical response as outlined in [I 06](#) and [I 07](#).
- f Enrollment of patients in Cohorts 1 and 2 and randomization of patients in Cohort 3: IRT contact will be performed anytime during screening period for screening, prior to IMP administration for all other concerned visits and on or before Day 1 for enrollment/randomization.
- g Biweekly administration or, for alglucosidase alfa in Cohort 3 only, weekly administration (current stable dose). For all patients, all visits following V2 (Day 1) are calculated from the day of first infusion of investigational medicinal product (IMP) in 14-day increments with a window of \pm 7 days (in Cohort 3 participants, 7 day increments with a window of \pm 3 days for weekly (qw) alglucosidase alfa treatment) for infusions and safety assessments and \pm 14 days for all other assessments.
- h Female patients of childbearing potential only will have serum test for pregnancy at Screening, a urine β -hCG test up to 24 hours before D1 infusion and every 4 weeks thereafter.
- i Physical examination CRF will ask physician to record current muscle pain and cramps specifically at each PE assessment. Tanner stage will be assessed as part of the PE assessment at screening/baseline.
- j To be measured at screening/baseline, every 3 months up to Week 73 and then every 6 months until Week 145/EOS in all patients.
- k At every infusion. Vital signs include heart rate, systolic and diastolic blood pressure, respiratory rate, temperature, and oxygen saturation and are to be assessed prior to infusion, with each infusion rate change, at the end of the infusion and at the end of the post-infusion observation period. Collection windows are \pm 15 minutes.
- l 12-lead ECG after at least 15 minutes in supine position (if supine is feasible for the patient). Review should be done at the site in a timely manner to determine if there are any safety concerns and for clinical management of the patient. In addition, reading will be done by central reader for analyses purposes only.
- m 12-lead ECG after at least 15 minutes in supine position (in triplicate predose at Day 1 only) and prior to receiving IMP: 3 ECGs within 5 minutes will be performed with at least 1 minute between 2 replicates.
- n Biochemistry panel will include BNP and CK.

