6 STUDY DESIGN

6.1 DESCRIPTION OF THE STUDY

ACT14132 is a multi-stage, phase 2, open-label, multicenter, multinational, ascending dose cohort, repeated intravenous (IV) infusion study of avalglucosidase alfa in pediatric patients with IOPD who have been previously treated with alglucosidase alfa and demonstrated clinical decline (Stage 1) or sub-optimal clinical response (Stage 2) in specified respiratory function, motor skills, cardiac parameters, and/or new onset of ptosis.

Stage 1

- Cohort 1 – at least 5 IOPD patients will receive avalglucosidase alfa at 20 mg/kg qow for 6 months.
- Cohort 2 – at least 5 IOPD patients will receive avalglucosidase alfa at 40 mg/kg qow for 6 months.

Stage 2

- Cohort 3 – at least 10 IOPD patients will be randomized 1:1 to receive avalglucosidase alfa at the highest tolerated avalglucosidase alfa dose in Stage 1 (20 mg/kg qow or 40 mg/kg qow) or alglucosidase alfa treatment at current stable dose (defined by dose of alglucosidase alfa administered regularly for a minimum of 6 months immediately prior to study entry) for 6 months. The randomization will be stratified on gender.

The first 5 patients will be enrolled in the 20 mg/kg qow dose cohort. If determined safe by an independent DMC after the 3rd patient in the 20 mg/kg qow group (Cohort 1) has received the 3rd infusion of avalglucosidase alfa and after 5 patients have started treatment in Cohort 1, the next cohort of avalglucosidase alfa at higher dose (40 mg/kg qow) will be initiated (Cohort 2). Cohort 3 will be initiated after determination of the highest tolerated avalglucosidase alfa dose in Cohort 1 and Cohort 2 after at least 5 patients in Cohort 1 and at least 5 patients in Cohort 2 have received the 7th dose of avalglucosidase alfa (or completed Week 13 with a minimum of 6 infusions).

After completion of treatment for 6 months (Week 25) and data collection for the principal analysis, the patients will continue on long-term avalglucosidase alfa treatment and follow-up in the Extension Period for up to a total of 7 years in the study. Cohort 3 patients receiving alglucosidase alfa will have the option to switch to treatment with avalglucosidase alfa in the extension period or discontinue the study. The data cut-off for the primary analysis will be after the last patient in Cohort 3 has completed 6 months of treatment (Week 25).

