10.1.2.3 Weekly (alglucosidase alfa only)

The following will be performed every week starting at the date of the first infusion for patients in Stage 2 – Cohort 3, who are randomized to receive alglucosidase alfa treatment at current stable dose and who have been receiving weekly infusions of alglucosidase alfa regularly for a minimum of 6 months immediately prior to study entry:

- Vital signs (before, during, and following infusion: see [Section 1.2](#));
- Infusion of IMP;
- AE collection;
- Concomitant medications/therapies.

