2.4.3.2 Compliance

A given administration will be considered noncompliant if the patient did not take the planned dose of treatment as required by the protocol. Compliance to the treatment regimen will be monitored by site personnel during the study.

Treatment compliance for PAP will be analyzed using summary statistics in the safety population. Compliance is calculated as the total amount of drug actually taken by a patient divided by the total amount of drug expected to be taken multiplied by 100. The number and percentage of patients with noncompliance (missed 2 or more consecutive infusions, or missed \geq 20% of total doses in the treatment or extension period) will be provided.

Treatment compliance for ETP and overall study period will be summarized similarly.

Additional dose related non-compliance will be summarized as protocol deviations.

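### Two primary-period counting rules use the every-other-week interval: a weekly control who does not continue gains 7 days of exposure, and a weekly control can be flagged noncompliant after half the scheduled time off drug

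*Protocol*

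**What the plan says.** **Dosing schedule.** Protocol 1.2.1, footnote g, gives "Biweekly administration or, for alglucosidase alfa in Cohort 3 only, weekly administration (current stable dose"). Protocol 10.1.2.3 sets a separate weekly visit list for controls "who have been receiving weekly infusions of alglucosidase alfa regularly for a minimum of 6 months" before entry. Avalglucosidase alfa is always given every other week, 13 doses by Week 25 (Protocol 8.1.1). The infusion window is adapted to the schedule: 7 days either side for every-other-week dosing, 3 days for weekly dosing (Protocol 8.1 and 8.7.1).

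**Exposure.** For a patient who enters the extension, PAP exposure runs to the first extension dose. Otherwise it runs to the alternative end point, "or 14 days after the last dose date in PAP if the patient is not continuing in extension period" (Protocol 11.4.1; SAP 2.4.3.1 has the same rule). The SAP then groups PAP exposure as under 12 weeks, 12 to under 24 weeks, and 24 weeks or more.

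**Noncompliance.** Protocol 11.4.1.1 tabulates "The number and percentage of patients with noncompliance (missed 2 or more consecutive infusions not for safety cause, or missed" at least 20% of total doses). SAP 2.4.3.2 has "The number and percentage of patients with noncompliance (missed 2 or more consecutive infusions, or missed" at least 20%), without the safety exemption. The SAP also reports percent compliance, the amount taken over the amount expected.

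**Size.** In Cohort 3, "at least 10 IOPD patients will be randomized 1:1", so about 5 controls are planned. The number dosed weekly is not stated.

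**The concern.** The plan recognises weekly dosing when it sets infusion windows and visits, but not when it counts missed infusions or ends exposure. Because weekly dosing can occur in one arm only, any distortion falls on that arm. SAP 2.4 displays summaries by cohort and treatment arm, so the two randomised arms stand side by side. A reader may use these tables to judge whether the comparator was delivered as fully as avalglucosidase alfa. With about 5 controls, one child flagged because of the counting unit moves the arm's noncompliance percentage by 1/5 = 20 points.

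**Working it through.** **Plan's own figure.** Weeks 1, 3, ..., 25 give 13 every-other-week doses, as Protocol 8.1.1 states. Weekly dosing over Weeks 1 to 25 gives 25. The documents do not say whether a Week 26 dose is given, which would make 26.

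**Exposure for a patient who does not continue.** Duration = (last dose date − first dose date) + tail.

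| Last weekly dose | 14-day tail | 7-day tail | SAP category, 14-day / 7-day tail |
|---|---|---|---|
| Week 25 | 168 + 14 = 182 days | 168 + 7 = 175 days | 24 weeks or more / same |
| Week 23 | 154 + 14 = 168 days (24 weeks) | 154 + 7 = 161 days (23 weeks) | 24 weeks or more / 12 to under 24 |
| Week 11 | 70 + 14 = 84 days (12 weeks) | 70 + 7 = 77 days (11 weeks) | 12 to under 24 / under 12 |

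The excess is always 7 days, which is 7/175 = 4.0% for a Week 25 completer. For an arm of 5 with 182 days each (910 days), one such child adds 7/910 = 0.77%. All five would add 35/910 = 3.85%.

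For a patient who continues, exposure ends at the Week 27 dose (Day 183), giving 182 days on either schedule; the tail is not used.

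**The two noncompliance criteria.**

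| | Every other week (13) | Weekly (25) |
|---|---|---|
| 2 consecutive misses, scheduled days | 2 × 14 = 28 | 2 × 7 = 14 |
| 2 misses as share of doses | 2/13 = 15.4% | 2/25 = 8.0% |
| Misses needed for 20% | 3 (23.1%) | 5 (20.0%) |

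**A single interruption.** Assume a uniform start and every due infusion in the interruption missed. Fourteen days always contain two weekly due dates and never two every-other-week due dates, so 100% against 0% are flagged. At 21 days the figures are 100% against 7/14 = 50%.

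If late dosing within the window is used, an infusion is missed only when the interruption also covers the 3 or 7 days after its due date. At 14 days, two weekly misses then need the first due date within 4 days of the start: 4/7 = 57%, against 0% every other week. At 21 days it is 100% against 0%. If early dosing is also used, the 14-day weekly figure falls to 1/7 = 14%.

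**The whole rule under independent misses.** The rates of 5% and 10% per infusion are assumptions. The probability of at least one run of 2 misses, or of reaching the 20% count, was computed exactly by tracking run length and total misses dose by dose.

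| | 5% misses | 10% misses |
|---|---|---|
| Run of 2 alone: weekly / every other week | 5.6% / 2.8% | 19.9% / 10.5% |
| 20% criterion alone: weekly / every other week | 0.7% / 2.5% | 9.8% / 13.4% |
| Whole rule: weekly / every other week | 5.8% / 4.2% (0.0584 / 0.0416) | 23.0% / 17.2% (0.2297 / 0.17154) |
| Whole rule, weekly, with a run of 4 instead of 2 | 0.7% | 9.8% |

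If all 5 controls were weekly, the excess expected number flagged is 5 × (0.0584 − 0.0416) = 0.08 at 5% and 5 × (0.2297 − 0.1715) = 0.29 at 10%.

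**The case against.** The case for leaving the text alone is that little depends on it, and most of that case stands. No per-protocol population is defined, the Cohort 3 efficacy set is mITT, and no test uses the flag or the exposure duration. The SAP's percent compliance, the number of infusions and the cumulative dose already scale with the schedule. Exposure duration is a calendar measure that disregards unplanned interruptions, so it was never a count of days covered by drug.

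Four stronger readings are tempting, and the documents do not support them:

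- *Every weekly control is credited with an extra week.* The tail applies in the PAP only to those who do not continue. The 14-day tails for the extension and for overall exposure concern avalglucosidase alfa, always given every other week, and are correct.
- *The noncompliance rule as a whole assumes every-other-week dosing, doubling a weekly child's chance of a flag.* Doubling is roughly true of the consecutive criterion alone. The 20% criterion works the other way in whole doses (3 of 13 against 5 of 25), and the ratio for the whole rule is about 1.3 to 1.4.
- *A two-week interruption always flags a weekly child.* That holds only if every due infusion is missed and the window is not used.
- *The efficacy comparison is biased.* No efficacy analysis takes either quantity as input.

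The objection does not remove the mismatch itself. The window was adapted to weekly dosing, these two rules were not, and no reason is given.

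**Conclusion.** The point holds in a limited form. The 14-day PAP tail is 7 days too long for a weekly control who does not enter the extension, and at the boundaries it can move that child up one SAP exposure category. The consecutive-miss criterion corresponds to half the scheduled time without drug on weekly dosing (14 against 28 days), so a two-week interruption can flag a weekly control but not an every-other-week child. Over the whole rule the gap is modest under independent misses.

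These sizes rest on assumed miss rates of 5% and 10%, on 25 planned weekly infusions, and on an unknown number of weekly controls (0 to all of about 5). If no control is dosed weekly, nothing changes. The effect is confined to descriptive tables, so this is a change to consider and does not threaten the trial's conclusions.

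**What to change.** 1. **Exposure (Protocol 11.4.1, SAP 2.4.3.1).** For PAP patients who do not continue, replace the fixed 14 days with one dosing interval after the last dose: 7 days if weekly, 14 days if every other week. Leave the extension and overall tails unchanged.
2. **Noncompliance (Protocol 11.4.1.1, SAP 2.4.3.2).** Choose one of two options:
   - State the consecutive criterion as 28 or more scheduled days without drug, which is 2 consecutive misses every other week and 4 weekly. This equalises block interruptions. It lowers the weekly flag rate for sporadic misses to 0.7% and 9.8%, below the every-other-week 4.2% and 17.2%, so it is partly a choice of metric and the SAP should say so.
   - Keep the criterion and report the flag by dosing schedule, beside percent compliance.
3. **In the same edit,** state how many weekly infusions are planned in the PAP (25 or 26), since this is the denominator of the 20% criterion. Also reconcile the safety exemption, which is in the protocol and missing from the SAP.

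The cost is a few lines of wording and one derivation by schedule. A control's schedule must already be known to apply the infusion window. No dosing or clinical rule changes.
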